**Duration of Exposure:**

The frequency of duration of exposure will be summarized using the following categories:

- 1-7 Days
- > 1-2 Weeks
- > 2-4 Weeks
- > 4-6 Weeks
- > 6-8 Weeks
- > 8-10 Weeks
- >10-12 Weeks
- > 12-14 Weeks
- > 14-16 Weeks
- > 16-18 Weeks
- > 18-20 Weeks
- > 20-26 Weeks
- > 26-52 Weeks
- > 52-104 Weeks
- > 104 Weeks (24 Months)

Subject-years of exposure will be calculated by summing the overall exposure for each subject within the dose group dividing by 365.25.

The number of tablets taken per subject will be summarized as a continuous variable. The total number of tablets taken will be determined by subtracting the total number of tablets returned and reported lost from the total number of tablets dispensed.

Continuous summaries of mean daily dose will also be presented. The mean daily dose level (mg) of ESL will be calculated as the total number of tablets taken within each treatment interval multiplied by the tablet strength, and then divided by the duration (in days) of treatment within the treatment interval. The overall mean daily dose will be calculated as the weighted average of the treatment intervals (i.e., the sum of the non-missing mean daily doses for each treatment interval multiplied by their respective number of days in the interval, divided by the total number of days in the

intervals with non-missing mean daily doses).

Descriptive statistics will be used to summarize percent compliance. Further, the number and percent of subjects that are <80%, 80-120% or >120% will be displayed.

Percent compliance will be derived as the number of tablets taken divided by the number of tablets that should have been taken, expressed as a percent.

Listing of subject treatment exposure and compliance will be provided. In addition, listing of study drug dosing and study drug accountability including number of tablets dispensed, returned, lost/missing, taken will be provided.

## 7.6 Efficacy Analyses

ITT population will be used for all the efficacy analyses. For the analysis of seizure data, listing of seizure symptoms, seizure diary, and SSF and related derived parameters will be provided.

### **Time on eslicarbazepine acetate monotherapy**

Kaplan Meier methods will be used to estimate the median time (and 95% CI) on eslicarbazepine acetate monotherapy for both 1-Year Open-Label Period and Post-1-Year Open-Label Period.

For the 1-Year Open-Label Period, time on monotherapy as defined in Section 5.2.2 will be used for analysis. Subjects who were still taking only eslicarbazepine acetate as monotherapy at the end of the 1-Year Open-Label Period of study will be censored at the last dose of the 1-Year Open-Label Period. Subjects who withdrew during the 1-Year Open-Label Period will also be censored at the time of the last known dose before the withdrawal. Subject who added a non-rescue AED will be an event on the date of the start AED during 1-Year Open-Label Period.

For the Post-1-Year Open-Label Period, time on monotherapy as defined in Section 5.2.3 will be used for analysis. Subjects who were still taking only eslicarbazepine acetate as monotherapy at the end of the Post-1-Year Open-Label Period will be censored at the last dose of the Post-1-Year Open-Label Period. Subjects who withdrew during the Post-1-Year Open-Label Period will also be censored at the time of the last known dose before the withdrawal. Subject who added a non-rescue AED will be an event on the date of the start AED during Post-1-Year Open-Label Period.

Subjects who never started the monotherapy treatment period in protocol 093-045 or 093-046 will not be included in this analysis. Change in dosage levels from protocol 093-045 or 093-046, dosage changes during protocol 093-050, and the time gap between the parent studies and the extension study will be ignored.

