### 5.2.2. 1-Year Open-Label Period Efficacy Endpoints

#### 1. Time on eslicarbazepine acetate monotherapy

Time on eslicarbazepine acetate monotherapy during 1-Year Open-Label Period will be calculated from the date of the first eslicarbazepine acetate monotherapy dose in protocol 093-045 or 093-046 (Visit 6/Week 8) to the last known dose of eslicarbazepine acetate monotherapy during 1-Year Open-Label Period as follows;

- a. For a subject who added a non-rescue AED during 1-Year Open-Label Period, Time on Monotherapy during 1-Year Open-Label Period is calculated as the date of start a non-rescue AED during 1 Year Open-Label Period minus the date of the first monotherapy dose in protocol 093-045 or 093-046.
- b. For a subject who completed the 1-Year Open-Label Period, and did not add any non-rescue AED since the date of the first monotherapy dose in protocol 093-045 or 093-046, Time on Monotherapy during 1-Year Open-Label Period is calculated as the date of the last known dose during 1-Year Open-Label Period, minus the date of the first monotherapy dose in protocol 093-045 or 093-046, plus 1.
- c. For a subject who did not complete the 1-Year Open-Label Period, and did not add any non-rescue AED since the date of the first monotherapy dose in protocol 093-045 or 093-046, Time on Monotherapy during 1-Year Open-

Label Period is calculated as the date of the known dose before the withdrawal during 1-Year Open-Label Period, minus the date of the first monotherapy dose in protocol 093-045 or 093-046, plus 1.

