**8. Treatment retention time (time to withdrawal due to lack of efficacy or adverse events).**

If a subject's reason for withdrawal from 1-Year Open-Label Period included: withdrawal of consent, lost to follow-up, physician decision or other, then it will be assumed the subject terminated due to lack of efficacy. For subjects that discontinue due to adverse event or lack of efficacy, the treatment retention time during the 1-Year Open-Label Period will be calculated as the date of last known dose during the 1-Year Open-Label Period minus the date of the first dose of eslicarbazepine acetate monotherapy in protocol 093-045 or 093-046 (Visit 6/Week 8), plus 1. The time may include taking eslicarbazepine acetate concomitantly with other AEDs.

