**Treatment retention**

Kaplan Meier methods will be used to estimate the median retention time (and 95% CI) on eslicarbazepine acetate for subjects who discontinued early due to adverse event(s) or lack of efficacy for both 1-Year Open-Label Period and Post-1-Year Open-Label Period.

For 1-Year Open-Label Period, subjects who discontinued the study not due to those reasons (i.e. protocol deviation) as defined in Section 5.2.2 will be censored at the date of the last known dose during 1-Year Open-Label Period. Subjects who were still taking eslicarbazepine acetate at the end of the 1-Year Open-Label Period of study will be censored at the last dose of the 1-Year Open-Label Period.

For Post-1-Year Open-Label Period, subjects who discontinued the study not due to those reasons (i.e. protocol deviation, study drug became available in subject's locale, and sponsor terminates clinical study) as defined in Section 5.2.3 will be censored at the date of the last known dose during Post-1-Year Open-Label Period. Subjects who were still taking eslicarbazepine acetate at the end of the Post-1-Year Open-Label Period of study will be censored at the last dose of the Post-1-Year Open-Label Period.

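### Time on monotherapy censors every withdrawal, so its Kaplan-Meier curve overstates how long subjects actually stayed on monotherapy

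*SAP*

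**What the plan says.** SAP Section 5.2.2, item 1, measures time on monotherapy from the first monotherapy dose in the parent study "to the last known dose of eslicarbazepine acetate monotherapy during 1-Year Open-Label Period". For a subject who adds a non-rescue AED, time stops when that AED starts. For everyone else, completers and non-completers alike, it runs to the last known dose. Section 5.2.3, item 3, does the same for the post-1-year period.

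Section 7.6 then assigns event status:
- Method: "Kaplan Meier methods will be used to estimate the median time (and 95% CI) on eslicarbazepine acetate monotherapy", for both periods.
- Event: "Subject who added a non-rescue AED will be an event on the date of the start AED during 1-Year Open-Label Period".
- Withdrawals in year 1: "Subjects who withdrew during the 1-Year Open-Label Period will also be censored at the time of the last known dose before the withdrawal".
- Withdrawals after year 1: "Subjects who withdrew during the Post-1-Year Open-Label Period will also be censored at the time of the last known dose before the withdrawal".

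Retention time is a separate endpoint. Section 7.6 estimates it "for subjects who discontinued early due to adverse event(s) or lack of efficacy for both 1-Year Open-Label Period and Post-1-Year Open-Label Period". Sections 5.2.2 (item 8) and 5.2.3 (item 4) widen that group. If the reason is loss to follow-up, withdrawn consent, a physician's decision or other, "then it will be assumed the subject terminated due to lack of efficacy". Only protocol deviation stays censored on withdrawal in year 1; after year 1, so do local availability of the drug and termination by the sponsor.

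No competing-risk analysis is planned. The only additional efficacy analysis, on the per-protocol population (Section 7.1), changes the subjects and not the event rule.

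**The concern.** A subject who stops eslicarbazepine is no longer on monotherapy. Censoring at that point asks Kaplan-Meier to assume that the subject would have gone on like those who remained. That answers a different question: how long until an AED is added, if nobody could withdraw. Under the label 'time on monotherapy', a reader will take it as the time that subjects actually spent on the drug alone.

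The censoring is also unlikely to be neutral. In the retention endpoint the SAP counts adverse-event and lack-of-efficacy withdrawals as failures, and assumes lack of efficacy for several less specific reasons. Its seizure-free endpoint (Section 5.2.2, item 5) likewise counts subjects who discontinue before Visit 7 as not seizure-free. Maintenance of effect is a stated secondary objective (Section 2.2), and time on monotherapy is the first efficacy endpoint listed.

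**Working it through.** **Inputs.** The SAP gives no expected median, event count or rate for this endpoint, and Section 3.3 places the sample size outside statistical considerations, so there is no planned figure to reproduce. Event and censoring rules come from Section 7.6. Follow-up in the 1-year analysis is 10 weeks of parent-study monotherapy (Section 6.5) plus 52 weeks: 62 weeks, about 14 months or 1.2 years, ignoring any gap between studies. All rates below are assumptions.

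**Step 1: direction, without rates.** Kaplan-Meier multiplies factors (1 − d/n) at event times. Recoding a censored withdrawal as an event leaves the follow-up times and risk sets unchanged and only adds factors below 1. The curve can fall or stay the same; it cannot rise.

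**Step 2: size at 1 year.** Let a be the proportion whose monotherapy ends by an added AED within 1 year, and w the proportion who withdraw as failures while still on monotherapy. Assume constant hazards and no other losses.
- Total hazard: H = −ln(1 − a − w)
- AED hazard: h = H × a/(a + w)
- Planned curve at 1 year: exp(−h); actually on monotherapy: 1 − a − w
- Medians: ln 2/h (planned) and ln 2/H (withdrawals counted)

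For a = 0.15 and w = 0.20: H = −ln 0.65 = 0.4308; h = 0.4308 × 0.15/0.35 = 0.1846; exp(−0.1846) = 0.83; medians 0.6931/0.1846 = 3.8 and 0.6931/0.4308 = 1.6 years.

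| a / w | Planned curve, 1 year | Actually on monotherapy | Planned median (years) | Median, withdrawals counted (years) |
|---|---|---|---|---|
| 10% / 10% | 89% | 80% | 6.2 | 3.1 |
| 15% / 20% | 83% | 65% | 3.8 | 1.6 |
| 20% / 30% | 76% | 50% | 2.5 | 1.0 |

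**Step 3: which medians would be seen.** Against about 1.2 years of follow-up, five of these six medians would not be reached in the 1-year analysis; only the 1.0-year value would. The post-1-year analysis starts from the same first monotherapy dose but runs longer, so a difference in medians could appear there.

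**Step 4: wider range.** Now take 12-month net risks (each cause acting alone) of 15% to 50% for AED addition and 10% to 40% for failure withdrawal. With monthly hazards α and ω, the ratio of medians is (α + ω)/α, which runs from 1.15 (50%, 10%) to 4.14 (15%, 40%). At 25% and 30%, α = −ln(0.75)/12 = 0.0240 and ω = −ln(0.70)/12 = 0.0297. The medians are 28.9 and 12.9 months, and the 12-month proportions are 0.75 and 0.75 × 0.70 = 0.525.

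**Step 5: if withdrawal and need for an AED are linked.** A simulation of 20,000 subjects used the 25%/30% hazards, 60 months of follow-up and a shared gamma frailty.

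| Frailty variance | Planned median (months) | True median time to AED | Median, withdrawals counted | 12 months: planned / true AED-free / on monotherapy |
|---|---|---|---|---|
| 0 | 28.9 | 28.9 | 12.9 | 0.75 / 0.75 / 0.53 |
| 0.5 | 43.8 | 34.8 | 15.4 | 0.78 / 0.77 / 0.57 |
| 1.0 | not reached | 42.4 | 18.5 | 0.80 / 0.78 / 0.61 |

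With independence, the planned rule is right for time to an added AED and wrong only for actual time on monotherapy. With a positive link it is too high for both. At 12 months, though, the link itself adds at most about 0.02; most of the gap comes from what is counted as an event.

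**The case against.** The strongest reply is that these are two endpoints with two purposes. Retention may include time on added AEDs; time on monotherapy may not. Different event definitions are then to be expected, and if the target is time to the first added AED and withdrawal is independent of it, the planned estimate is unbiased. This stands as far as it goes: the difference from retention is not in itself a contradiction. It does not rescue the label, and independence sits badly with the SAP's own treatment of the same reasons under retention.

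Several stronger readings are tempting but not supported:
- **That Sections 5.2.2 and 7.6 contradict each other.** Section 5.2.2 fixes a duration, not event status. Its last-known-dose rule also covers completers, who are properly censored.
- **That all the same subjects are failures in one analysis and censored in the other.** Protocol-deviation withdrawals are censored in both, as are local availability and sponsor termination after year 1. A subject who adds an AED and later withdraws is already a monotherapy event.
- **That AED addition and withdrawal are always the same failure.** Section 3.1 ties AED addition to clinically significant seizure worsening together with non-response to, or intolerance of, a dose increase. It does not show that withdrawal for an adverse event alone is the same thing. Subjects discontinued for needing more than two additional AEDs have already had their event.
- **That event status turns on whether a replacement AED starts just before or just after the termination visit.** The documents do not say how such starts are dated or classified.

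It is also fair to say that this is a secondary, descriptive endpoint in an uncontrolled safety extension, and that withdrawals remain visible in the disposition, completion and retention outputs. Those outputs do not correct the monotherapy estimate.

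**Conclusion.** The concern holds as a problem of event definition and labelling, and should be fixed. The direction is certain: the planned curve cannot lie below the curve for actual time on monotherapy, and lies above it once any subject still on monotherapy withdraws for an adverse event or lack of efficacy. The size cannot be found from the documents. Under the three assumed pairs of rates with constant hazards, the overstatement at 1 year is 9, 18 and 26 percentage points (89 − 80, 83 − 65, 76 − 50).

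A reader might infer that the reported 1-year median will be inflated by a known factor. That is not supported: the rates are assumed, and with about 14 months of follow-up most medians would not be reached. Nor does the point touch the primary objective, which is safety, so it does not call for a critical rating.

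**What to change.** In SAP Section 7.6, for both periods:
- Count as the event the first of (i) the start of a non-rescue AED and (ii) the last dose before withdrawal for adverse event or lack of efficacy.
- Censor completers, protocol-deviation withdrawals, sponsor termination and local availability, as the retention analysis does.
- Show the result with and without the reassignment of vaguer withdrawal reasons to lack of efficacy (Sections 5.2.2, item 8, and 5.2.3, item 4). That reassignment is a worst-case assumption and should not silently drive the estimate. Without it, those subjects are censored.
- Keep the current rule only as a secondary analysis labelled 'time to added AED', preferably as a cumulative incidence with withdrawal as a competing event.
- Give the proportion on monotherapy at 1 year beside the median, since the median may not be reached.

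Align the wording of Section 5.2.2, item 1, and Section 5.2.3, item 3. The cost is a changed event flag, a few extra runs and a shorter, less favourable estimate. The dates and withdrawal reasons needed are already used by the planned analyses.

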### **Seizure standard frequency (SSF)**

Descriptive statistics will summarize the SSF for 1 week, 1 month, each 3 month visit window of time, overall, and by the following subgroups: number of baseline AEDs,

and baseline AED medications, and seizure type.

**Relative (%) change from baseline in SSF**

Relative (%) change from baseline in SSF will be summarized descriptively for 1 week, 1 month, each 3-month visit window, overall, and by the following subgroups: number of baseline AEDs, and baseline AED medications, seizure type. The number and percentage of subjects with the category in Section 5.2.2 will also be presented.

**Responder rate**

The number and proportion (%) of responders with 95% confidence intervals (using binomial methods) will be presented for 1 week, 1 month, each 3-month visit window, overall, and by the following subgroups: number of baseline AEDs, and baseline AED medications.

**Seizure-free**

The number and proportion (%) of subjects that are seizure-free with 95% confidence intervals (using binomial methods) will be presented for 1 week, 1 month, each 3-month visit window and overall.

**Completion rate**

The number and proportion (%) of subjects completing the 1-Year Open-Label Period and Post-1-Year Open-Label Period will be provided along with a 95% confidence interval (using binomial methods).

**Treatment retention**

Kaplan Meier methods will be used to estimate the median retention time (and 95% CI) on eslicarbazepine acetate for subjects who discontinued early due to adverse event(s) or lack of efficacy for both 1-Year Open-Label Period and Post-1-Year Open-Label Period.

For 1-Year Open-Label Period, subjects who discontinued the study not due to those reasons (i.e. protocol deviation) as defined in Section 5.2.2 will be censored at the date of the last known dose during 1-Year Open-Label Period. Subjects who were still taking eslicarbazepine acetate at the end of the 1-Year Open-Label Period of study will be censored at the last dose of the 1-Year Open-Label Period.

For Post-1-Year Open-Label Period, subjects who discontinued the study not due to those reasons (i.e. protocol deviation, study drug became available in subject's locale, and sponsor terminates clinical study) as defined in Section 5.2.3 will be censored at the date of the last known dose during Post-1-Year Open-Label Period. Subjects who were still taking eslicarbazepine acetate at the end of the Post-1-Year Open-Label Period of study will be censored at the last dose of the Post-1-Year Open-Label Period.

### **Change in Quality of Life in Epilepsy (QOLIE-31)**

Values and change from baseline (Visit 2, Day 0 from protocol 093-045 or 093-046) in the seven individual items, overall score, and global assessment will be summarized with descriptive statistics for each visit. A listing of subjects with QOLIE-31 assessments will be provided.

### **Change in Montgomery-Asberg Depression Rating Scale (MADRS)**

The total MADRS score and the 10 individual items will be summarized descriptively for each evaluation visit, along with the change from baseline (Visit 2, Day 0 from protocol 093-045 or 093-046).

In addition, this analysis will be repeated for those subjects with a MADRS score of  $\geq 14$  at screening (Visit 1) of this study. A listing of subjects with MADRS assessments will be provided.

### **Patient Global Impression (PGI)**

The total PGI score and the 5 individual items will be summarized descriptively from Visit 8 every three months during the Post-1-Year Open-Label Period, until the End of Study or Early Termination Visit.

Listing of Patient Global Impression (PGI) will be provided.

## **7.7 Safety Analyses**

Safety outcomes will be analyzed descriptively. Safety variables will include adverse events, vital sign measurements, orthostatic effects, clinical laboratory evaluations (serum chemistry, hematology, and urinalysis), thyroid function, lipid levels, coagulation testing, and bone turnover markers, body weight, blood sodium levels, ECG readings, and C-SSRS.

### **7.7.1 Adverse Events**

The following TEAEs will be summarized by MedDRA SOC and PT:

- All AEs (including number of events and subject incidence)
- AEs by severity (mild, moderate, severe)
- All serious adverse events (SAE)
- All AEs by relationship to treatment (unrelated, or potentially related)
- AEs leading to death
- AEs leading to discontinuation

All above AEs and the AE subgroup analyses in Section 6.5 will be summarized for the three periods as below.

- Year Open-Label Period
- Post-1-Year Open-Label Period
- Combined 1-Year Open-Label Period and Post-1-Year Open-Label Period

A listing of AEs, serious AEs, and AEs leading to discontinuation or death will be presented as appropriate.

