### 2.1. Primary objective

To evaluate the 1-Year Open-Label Period and Post-1-Year Open-Label Period safety and tolerability of eslicarbazepine acetate flexible dosing within the range of 800 mg to 2400 mg in subjects with partial epilepsy who have participated in an 18-week double-blind eslicarbazepine acetate monotherapy study (Protocols 093-045 or 093-046).

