## 3. Study design

### 3.1. General Description

This study is a long-term, multicenter, open-label, safety extension study in male and female subjects (aged 16 to 70 years, inclusive) with partial onset seizures who have just completed, discontinued, or exited the 18-week treatment phase of Protocols 093-045 or 093-046. The initial study duration is 1-Year Open-Label Period with the option of continuing study drug treatment Post-1-Year Open-Label Period until a subject discontinues study, the study drug becomes clinically available in the subject's locale, or the sponsor terminates the study drug clinical development program.

This study will evaluate the safety and maintenance of effect of long-term eslicarbazepine acetate treatment at flexible doses in the range of 800 mg to 2400 mg once-a-day (QD) over a 1-Year Open-Label Period and a Post-1-Year Open-Label Period.

[figure not shown]

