### 5.3.2. Safety Endpoints

#### Adverse Events

All AEs will be coded using Medical Dictionary for Regulatory Activities (MedDRA), Version 13.1.

Treatment-emergent adverse events (TEAEs) will be defined as:

- AEs that occurred on or after the first dose of study drug during this protocol,
- AEs with a missing start date and a stop date on or after the first dose of study drug during this protocol, or
- AEs with both a missing start and stop date.

Adverse events whose relationship is assessed as “not related” will be grouped as “unrelated.” Otherwise, adverse events assessed as “unlikely,” “possible,” “probable,” or “definite,” unknown or missing will be grouped as “potentially related.” Further, if a subject reports more than one AE within the same treatment regimen, system organ class (SOC) and preferred term (PT), and any are related, it will be summarized as related.

If a subject has more than one occurrence of an event within a SOC and/or PT, the subject incidence summaries will count each subject only once within that SOC and/or PT. In the case of more than one event within a SOC and/or PT, the event with the highest severity will be summarized in the by-severity summaries and the one with the strongest relationship will be summarized in the by-relationship summaries.

TEAEs will be sorted by SOC in alphabetical order and then by PT sorted by decreasing frequency, with preferred terms with the same frequency sorted in alphabetical order.

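### TEAEs in the 1-Year, Post-1-Year and combined periods are summarised only as event counts and crude subject incidence, so side-by-side percentages depend on follow-up length, dropout and denominator as well as on risk

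*SAP*

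**What the plan says.** The primary objective in SAP section 2.1 covers both periods: "To evaluate the 1-Year Open-Label Period and Post-1-Year Open-Label Period safety and tolerability". Section 3.1 sets the first period at one year and lets subjects continue "until a subject discontinues study, the study drug becomes clinically available" in their locale, or the sponsor ends the development programme. Post-1-Year follow-up therefore has no fixed end and differs between subjects.

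For adverse events, section 7.7.1 says "All above AEs and the AE subgroup analyses in Section 6.5 will be summarized for the three periods as below", and lists the 1-Year, the Post-1-Year and the combined period. The measures are the number of events and the subject incidence. Under section 5.3.2, "the subject incidence summaries will count each subject only once within that SOC and/or PT", whatever the subject's time at risk. Section 6.1 makes categorical summaries counts and percentages, and section 7.7 makes the safety analysis descriptive.

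Section 7.5 does plan person-time: "Subject-years of exposure will be calculated by summing the overall exposure for each subject within the dose group dividing by 365.25". This is overall exposure by mean-daily-dose group. It is not split by period, and no adverse-event summary uses it.

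Two definitions are absent. Section 7.1 assigns all safety analyses to the ITT population and gives no separate adverse-event denominator for the Post-1-Year period. Section 5.3.2 defines treatment emergence but does not say to which period an event belongs.

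**The concern.** A crude percentage over an open-ended period rises with follow-up even if the risk per unit of time never changes. It falls when subjects leave early, and it falls again if subjects who never entered the period stay in the denominator. These influences act differently on the three columns of the planned tables. Someone reading across a row could take a change in follow-up for a change in risk, or miss a real change.

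These tables are the main adverse-event output for the primary objective. Elsewhere the SAP does allow for time: seizures are standardised to 28 days (section 5.2.2), and time on monotherapy and treatment retention use Kaplan-Meier methods with censoring (section 7.6). For responder and seizure-free rates, section 5.2.2 uses ITT subjects who enter the interval as the denominator. Adverse-event incidence has no time adjustment and no such entrant rule.

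**Working it through.** **No figure to reproduce.** SAP section 3.3 places the sample size outside statistical considerations. Neither document gives an adverse-event rate, a follow-up distribution or a subject-year total. What follows is an illustration, and every rate, entry fraction, dropout hazard and follow-up time in it is an assumption.

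**What the documents show about follow-up length.** Post-1-Year visits are 3 months apart from Visit 8 at month 15 (SAP section 5.1). The schedule's footnotes run to Visit 13 and beyond, and Visit 13 is month 15 + 5 × 3 = 30. The top exposure category in section 7.5 is open above 104 weeks. The Post-1-Year period was added on 17 August 2010 (Protocol, Amendment 4) and the SAP is dated 19 May 2017, a gap of about 6.75 years. That is a calendar ceiling only. Neither date is an entry or last-visit date.

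**Model.** Constant hazard λ of a first event within a period, with 10% incidence in a fully followed year 1: λ = -ln(1 - 0.10) = 0.1054, or 10.5 per 100 subject-years.

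**Scenario A: entrants as denominator, no dropout.** Incidence over T Post-1-Year years = 1 - exp(-λT). The combined period replaces T by 1 + T.

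| Post-1-Year follow-up T (years) | 1-Year % | Post-1-Year % | Combined % | Rate per 100 subject-years, every period |
|---|---|---|---|---|
| 0.5 | 10.0 | 5.1 | 14.6 | 10.5 |
| 1 | 10.0 | 10.0 | 19.0 | 10.5 |
| 2 | 10.0 | 19.0 | 27.1 | 10.5 |
| 3 | 10.0 | 27.1 | 34.4 | 10.5 |
| 5 | 10.0 | 41.0 | 46.9 | 10.5 |

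At 3 years the ratio is 27.1/10.0 = 2.7 with no change in risk.

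**Scenario B: dropout, and the ITT denominator of section 7.1.** Let a fraction c of subjects enter the Post-1-Year period, with year-1 dropout hazard d = -ln(c) and Post-1-Year dropout hazard 0.15 per year. Incidence = λ/(λ + d) × (1 - exp(-(λ + d)T)). The Post-1-Year percentage of ITT is c times the percentage of entrants.

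- Year 1, c = 0.5: d = 0.693, and 0.1054/0.7985 × (1 - exp(-0.7985)) = 7.3%.
- Year 1, c = 0.8: d = 0.223, and 0.1054/0.3285 × (1 - exp(-0.3285)) = 9.0%.
- Post-1-Year, entrants, T = 3: 0.1054/0.2554 × (1 - exp(-0.7661)) = 22.1%.
- Post-1-Year, entrants, T = 1: 0.1054/0.2554 × (1 - exp(-0.2554)) = 9.3%.

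| Entry c | T (years) | 1-Year % of ITT | Post-1-Year % of ITT | Ratio |
|---|---|---|---|---|
| 0.5 | 1 | 7.3 | 4.6 | 0.64 |
| 0.5 | 3 | 7.3 | 11.0 | 1.5 |
| 0.8 | 3 | 9.0 | 17.7 | 2.0 |

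The rate is 10.5 per 100 subject-years throughout. Ratios use unrounded values.

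Changing the denominator alone does not cure this. At 3 years the entrant figure of 22.1% against 7.3-9.0% in year 1 gives ratios of about 2.5-3.0.

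**Scenario C: a real fall.** As in A, but the hazard halves after year 1 to 5.3 per 100 subject-years. The Post-1-Year percentage is 5.1% at 1 year, 10.0% at 2, 14.6% at 3 and 23.2% at 5, against 10.0% in year 1. Beyond 2 years a halved risk appears as an increase.

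**The case against.** The strongest reply is that the study is a descriptive extension. Section 2.1 says safety will be evaluated in two periods. No section defines a contrast or trend between them. A crude percentage is a valid statement of how many subjects had an event. That stands. A reader might infer that the plan contains a primary comparison of long-term with first-year risk, and that this comparison is biased. The documents contain no such comparison, so nothing here concerns a test or an error rate. What remains is that the periods are tabulated separately for the primary objective, and the percentages cannot safely be read across.

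A reader might also infer that crude percentages always make later risk look higher, by a factor near 2.7. That figure needs 3 years of follow-up, no dropout and entrants as denominator, whereas section 7.1 names the ITT population. Scenario B includes a ratio below 1. Nor do the documents show that subjects were followed for six years or more, or that follow-up differs between the subgroups in section 6.5. Distortion of subgroup results is possible but undocumented.

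There is partial mitigation. Event counts and total subject-years would allow a whole-study event rate, though not rates by period. Retention in section 7.6 is time-based, but it combines adverse-event withdrawal with lack of efficacy and counts from the first monotherapy dose in the parent study.

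Rates also have limits. Post-1-Year subjects are selected for having stayed through year 1, and one rate per period hides a changing hazard. Finally, only the protocol's amendment history is available, so its own adverse-event analysis text could not be checked.

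**Conclusion.** The point holds as a matter of interpretation. The planned percentages depend on follow-up, dropout and an incompletely specified Post-1-Year denominator, and the planned tables do not allow period-specific rates to be recovered. Under an unchanged hazard, the illustrated ratios of Post-1-Year to 1-Year percentages are about 2.7 (entrants, 3 years, no dropout), about 1.5-2.0 (ITT, 50-80% entry, 3 years) and about 0.64 (ITT, 50% entry, 1 year). The size and direction in this trial cannot be determined from the documents. No planned number is wrong and no data are lost. The change should be made because it is cheap and removes the mechanical dependence on follow-up length.

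**What to change.** In section 7.5, calculate subject-years separately for the 1-Year and Post-1-Year periods, as well as overall.

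In section 7.7.1:

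- Keep the crude percentages, with subjects who entered the Post-1-Year period as that column's denominator.
- Assign each TEAE to a period by its onset date relative to the start of the Post-1-Year period.
- For any TEAE, SAEs, TEAEs leading to discontinuation, deaths and the more frequent preferred terms, add the number of subjects with a first event in the period per 100 subject-years at risk. Do this for all three periods.
- Base any descriptive statement between periods on these rates. Note that Post-1-Year subjects are selected for having stayed through year 1, and that a single rate per period assumes a roughly constant hazard.

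This should need only dates that the planned summaries already use, and it removes no planned output. The cost is SAP wording and modest programming, since time at risk must be derived by subject, period and event category.
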